3.2 Eligibility: Inclusion Criteria

Important note: The inclusion criteria listed below are interpreted literally and cannot be waived. All clinical and laboratory data required for determining eligibility of a patient enrolled on this trial must be available in the patient's medical/research record. These source documents must be available for verification at the time of audit.

All clinical and laboratory studies to determine eligibility must be performed within 7 days prior to enrollment unless otherwise indicated. Laboratory values used to assess eligibility must be no older than seven (7) days at the start of therapy. Laboratory tests need not be repeated if therapy starts within seven (7) days of obtaining labs to assess eligibility. If a post-enrollment lab value is outside the limits of eligibility, or laboratory values are $>$ 7 days old, then the following laboratory evaluations must be re-checked within 48 hours prior to initiating therapy: CBC with differential, bilirubin, ALT (SGPT) and serum creatinine. If the recheck is outside the limits of eligibility, the patient may not receive protocol therapy and will be considered off protocol therapy. Imaging studies and bone marrow biopsy and/or aspirate, if applicable, must be obtained within 28 days prior to start of protocol therapy (repeat the tumor imaging if necessary).

3.2.1 Age: Patients must be \leq 30 years of age at the time of study entry.

3.2.2 Diagnosis:

- i. Cohort A: Patients must have a histologic diagnosis of infantile fibrosarcoma with an *NTRK1*, *NTRK2*, or *NTRK3* fusion identified in a CLIA/CAP certified laboratory. Fusions may be identified by FISH or molecular techniques (RT-PCR using primers flanking the fusion junction or next generation sequencing). For fusions identified by FISH, an *ETV6* rearrangement is sufficient for eligibility in Cohort A. Identification of the upstream TRK fusion partner is not required.
- ii. Cohort B: Patients must have a histologic diagnosis of any solid tumor other than infantile fibrosarcoma, including CNS tumors but excluding high grade gliomas. An *NTRK1*, *NTRK2*, or *NTRK3* fusion must be identified in a CLIA/CAP certified laboratory. Fusions may be identified by FISH or molecular techniques (RT-PCR using primers flanking the fusion junction or next generation sequencing). For fusions identified by FISH, there must be an identified rearrangement in *NTRK1*, *NTRK2*, or *NTRK3* (e.g., an *ETV6* rearrangement is **not** sufficient for eligibility) unless the patient has a diagnosis of congenital mesoblastic nephroma in which case an *ETV6* rearrangement is sufficient for eligibility. Identification of the upstream TRK fusion partner is not required.
- iii. Cohort C: Patients must have a histologic diagnosis of relapsed or refractory acute leukemia with an *NTRK1*, *NTRK2*, or *NTRK3* fusion identified in a CLIA/CAP certified laboratory. Fusions may be identified by FISH or molecular techniques (RT-PCR using primers flanking the fusion junction or next generation sequencing). For fusions identified by FISH, there must be an identified rearrangement in *NTRK1*, *NTRK2*, or *NTRK3* (e.g., an *ETV6* rearrangement is **not** sufficient for eligibility). Identification of the upstream TRK fusion partner is not required.

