1.3 Exploratory Aims

- 1.3.1 To determine the EFS, OS, and DoR of children with TRK fusion solid tumors other than IFS treated with adjuvant larotrectinib following upfront surgery with positive margins after neoadjuvant larotrectinib.
- 1.3.2 To determine the EFS, OS, and DoR of children with TRK fusion solid tumors who experience a complete response to larotrectinib and subsequently discontinue larotrectinib therapy
- 1.3.3 To determine the remission induction rate for patients with recurrent/refractory TRK fusion leukemia when treated with larotrectinib.
- 1.3.4 To evaluate the surgical morbidity and extent of resection of initially unresectable tumors in patients with TRK fusion solid tumors who undergo surgical resection following neoadjuvant larotrectinib.
- 1.3.5 To evaluate mechanisms of response and resistance to larotrectinib in children with TRK fusion cancers.
- 1.3.6 To evaluate the morphologic features of TRK fusion solid tumors at time of initial

biopsy to further define criteria for pathologic diagnosis of these tumors.

- 1.3.7 To evaluate immunohistochemistry for pan-TRK as a screening method for TRK fusion tumors and in resection specimens following neoadjuvant treatment with larotrectinib.
- 1.3.8 To evaluate the histologic response to larotrectinib in resection specimens following neoadjuvant treatment.
- 1.3.9 To evaluate circulating tumor DNA for the detection of the emergence of resistance mutations and recurrence in patients with TRK fusion solid tumors treated with larotrectinib.
- 1.3.10 To evaluate the ratio of CSF to concurrent plasma concentrations of larotrectinib in patients with leukemia.
- 1.3.11 To evaluate the change in neurocognitive/behavioral functioning over time between baseline and 5 years post-diagnosis of patients treated on this protocol using parent-reported adaptive functioning (ABAS-III General Adaptive Composite), executive function (BRIEF-P or BRIEF-2 Global Executive Composite Score), psychosocial functioning (BASC-3 Internalizing, Externalizing and Behavioral Symptoms Indices) and quality of life (PedsQL Total score).

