3.2.3 Disease Status

- i. Solid Tumors (Cohorts A & B): Patients must have measurable disease (see Section [10.3.1](#) for definition). Patients must have disease that cannot be completely resected without a predicted functional, neurologic, or significant cosmetic deficit in the opinion of the investigator.
- ii. Leukemia (Cohort C): Patients must have $\geq 5\%$ blasts in the bone marrow. Extramedullary disease is permitted.

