3.2.5 Prior Therapy

- Cohorts A & B: No prior anti-cancer therapy, including radiotherapy, other than surgical resection is permitted.
 - Patients who experience recurrence after surgery alone and no other anti-cancer therapy will be eligible.
 - If not eligible due to prior anticancer therapy, patients may be eligible for the larotrectinib arm of Pediatric MATCH (APEC1621A) or treatment with commercial larotrectinib off study.
- Cohort C: The following apply to patients with relapsed/refractory leukemia:
 - 3.2.5.1 Patients with relapsed leukemia (Cohort C) must have fully recovered from the acute toxic effects of all prior anti-cancer therapy and must meet the following minimum duration from prior anti-cancer directed therapy prior to enrollment. If after the required timeframe, the numerical eligibility criteria are met, e.g. blood count criteria, the patient is considered to have recovered adequately.
 - a. Cytotoxic chemotherapy or other anti-cancer agents known to be myelosuppressive. See DVL homepage for the Myelosuppressive, Non-Myelosuppressive, and Antibody Anti-Cancer Agents table (<https://cogmembers.org/Site/Disc/DevTherapeutics/Default.aspx>). For agents not listed, the duration of this interval must be discussed with the study chair and the study-assigned Research Coordinator prior to enrollment.
 - A waiting period prior to enrollment is not required for patients receiving standard cytotoxic maintenance chemotherapy (i.e., corticosteroid, vincristine, 6MP, and/or methotrexate).
 - A waiting period is not required for patients receiving a single dose of intrathecal methotrexate, hydrocortisone, and/or cytarabine within 7 days prior to enrollment
 - ≥ 14 days must have elapsed after the completion of other cytotoxic therapy, with the exception of hydroxyurea, for patients not receiving standard maintenance therapy. Additionally, patients must have fully recovered from all acute toxic effects of prior therapy.

Note: Cytoreduction with hydroxyurea must be discontinued ≥ 24 hours prior to the start of protocol therapy.

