3.3.1 Pregnancy or Breast-Feeding

Pregnant or breast-feeding women will not be entered on this study due to risks of fetal and teratogenic adverse events as seen in animal/human studies, *OR* because there is yet no available information regarding human fetal or teratogenic toxicities. Pregnancy tests must be obtained in girls who are post-menarchal. Female patients of reproductive potential may not participate unless they have agreed to use a highly effective contraceptive method for the duration of study therapy and for at least one month after the final dose of larotrectinib. Males of reproductive potential with a non-pregnant female partner of child-bearing potential must use a highly effective contraception for the duration of the study and for at least one month after the final dose of larotrectinib.

Because of the unknown risk of larotrectinib in nursing infants, nursing women should discontinue breastfeeding during treatment with larotrectinib and for 3 days following the final dose.

3.3.2 Concomitant Medications:

3.3.2.1 **Corticosteroids:** Patients with solid tumors, including CNS tumors, requiring corticosteroids who have not been on a stable or decreasing dose of corticosteroid for at least 7 days prior to enrollment are not eligible. Patients with leukemia may receive systemic corticosteroids for cytoreduction up to 24 hours prior to the start of protocol therapy. If used to modify **immune adverse events** related to prior therapy, ≥ 14 days must have elapsed since last dose of corticosteroid.

3.3.2.2 **Investigational Drugs:** Patients who are currently receiving another investigational drug are not eligible.

3.3.2.3 **Anti-cancer Agents:** Patients who are currently receiving other anti-cancer agents are not eligible [except leukemia patients receiving corticosteroids or hydroxyurea, which may be continued until 24 hours prior to start of protocol therapy]. Patients with leukemia should receive a single dose of intrathecal cytarabine, hydrocortisone, and/or methotrexate within 7 days prior to Day 1 of Cycle 1 at the time of the baseline lumbar puncture.

3.3.2.4 **Anti-GVHD agents post-transplant:** Patients who are receiving cyclosporine, tacrolimus or other agents to prevent graft-versus-host disease post bone marrow transplant are not eligible for this trial.

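### Cohort C can qualify on a marrow up to 28 days old with anti-leukemia therapy given after it, so a remission due to that therapy can be counted in the larotrectinib remission rate (aim 1.3.3)

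*Combined protocol and SAP*

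**What the plan says.** Section 3.2.3 admits a Cohort C patient whose marrow shows at least 5% blasts. Section 3.2 sets a general window, "All clinical and laboratory studies to determine eligibility must be performed within 7 days prior to enrollment unless otherwise indicated", and then a longer one for marrow: "Imaging studies and bone marrow biopsy and/or aspirate, if applicable, must be obtained within 28 days prior to start of protocol therapy". The repeat clause that follows, "repeat the tumor imaging if necessary", names imaging only, and the 48-hour recheck list covers blood counts and chemistry. The Cohort C schedule (4.4.2, item h) asks for a marrow before Cycle 1 and at its end, with no tighter window.

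The therapy rules for the same period are:

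- Steroids (3.3.2.1): "Patients with leukemia may receive systemic corticosteroids for cytoreduction up to 24 hours prior to the start of protocol therapy". Section 3.2.5.1(d) requires no wait before enrollment when they are given for cytoreduction.
- Hydroxyurea (3.2.5.1(a), 3.3.2.3): permitted until 24 hours before the start.
- Maintenance (3.2.5.1(a)): "A waiting period prior to enrollment is not required for patients receiving standard cytotoxic maintenance chemotherapy".
- Blinatumomab (3.2.5.1(c)): off for at least 3 days.
- Other cytotoxic therapy (3.2.5.1(a)): at least 14 "days must have elapsed after the completion of other cytotoxic therapy".

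The affected endpoint is exploratory aim 1.3.3: "To determine the remission induction rate for patients with recurrent/refractory TRK fusion leukemia when treated with larotrectinib".

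**The concern.** A remission induction rate is meant to describe the change from active leukemia at the first dose to remission afterwards. Here active leukemia may have been shown four weeks before the first dose, with effective treatment given in between. A patient whose marrow had already cleared, or was clearing, on Day 1 would meet the remission definition at the end of Cycle 1 and be reported as a larotrectinib remission.

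This matters because Section 2.5 states that leukemia patients have been on no earlier larotrectinib trial, so these few cases may be the main evidence. In a very small cohort one misattributed case carries great weight. If 3 to 5 patients are evaluable (an assumption; the documents give no Cohort C count), one case moves the rate by 1/5 to 1/3, or 20 to 33 percentage points.

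**Working it through.** **1. The plan's own figure.** The only numerical rule that could reach Cohort C is the two-stage design of 9.2, which 9.1 applies if nine evaluable patients of one histology enroll. The probability of declaring activity is the sum over x = 6 to 9 of P(X1 = x) × P(X2 ≥ 16 − x), with X1 ~ Bin(9, p) and X2 ~ Bin(12, p). At p = 0.60 this gives 0.0905, and at p = 0.85 it gives 0.9040. Both match the stated 9.05% and 90.40%.

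**2. How much therapy fits after the marrow.** Put the marrow on Day -28. Enrollment is 0 to 5 days before the first dose (3.1.5), and the 3.2.5.1 waiting periods run back from enrollment.

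| Therapy | Calculation | Days available |
|---|---|---|
| Steroid or hydroxyurea | 28 − 1 | 27 |
| Maintenance | 28 − 0 − (0 to 5) | 23 to 28 |
| Blinatumomab | 28 − 3 − (0 to 5) | 20 to 25 |
| Other cytotoxic | 28 − 14 − (0 to 5) | 9 to 14 |

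The qualifying marrow and the end-of-Cycle-1 marrow can be 28 + 28 = 56 days apart, with only the last 28 on larotrectinib.

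**3. Whether any rule compensates.**

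- Remission definitions (10.6.1 to 10.6.3 for AML, 10.7.1 and 10.7.2 for ALL) rest on the state reached: an M1 marrow, no circulating blasts or extramedullary disease, and a count category. None refers to therapy since baseline.
- Evaluability (9.4) needs one dose plus one of three conditions. None concerns intervening therapy.
- Section 4.1.4.1 bars other anti-cancer therapy, but only during protocol treatment.
- Section 10.3.4 attributes best response to larotrectinib alone, but it is a solid-tumor rule and excludes only surgery.

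**4. Possible size of the upward part.** Let p be the true larotrectinib remission rate, q the share of patients treated after the marrow, and r the chance that this treatment alone produces remission. The observed rate is p + (1 − p)qr. The documents give none of the three. I assume q = 25 to 75% and r = 20 to 40%, so qr = 0.05 to 0.30.

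- p = 20%: 0.20 + 0.80 × (0.05 to 0.30) = 24 to 44%.
- p = 40%: 0.40 + 0.60 × (0.05 to 0.30) = 43 to 58%.

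**5. If the two-stage rule applied.** At a true rate of 60% the observed rate is 0.60 + 0.40qr, and the chance of declaring activity becomes:

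| qr (assumed) | Observed rate | P(declare active) |
|---|---|---|
| 0 | 60% | 9.05% |
| 0.05 | 62% | 12.4% |
| 0.10 | 64% | 16.6% |
| 0.20 | 68% | 27.8% |
| 0.30 | 72% | 42.3% |

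**6. Why recoding is not the remedy.** Scoring every exposed remission as a failure, with all patients in the denominator, gives p(1 − q), an error of −pq. Leaving the rate as it is gives an error of +(1 − p)qr. Recoding is the larger error whenever r < p/(1 − p). That threshold is 0.67 at p = 40%, above every r assumed here. It is 0.25 at p = 20%. At p = 40% and q = 75%, recoding errs by −30 points, against +9 to +18 if nothing is done.

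**The case against.** The strongest reply is that little hangs on this. Aim 1.3.3 is exploratory, the synopsis says Cohort C will be reported descriptively, and Section 2.1.5 cites only four children with such fusions in one sequencing effort. Section 2.7.1 says accrual is complete. The formal rule is reached only with nine patients of one histology. All of this stands, and it keeps the point modest. It does not remove it: a descriptive rate is still read as the drug's effect.

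A reader might infer more than the documents support:

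- **That such remissions have been counted.** The plan permits it. Nothing shows that it happened, or how often.
- **That the bias can only be upward.** Recent cytotoxic therapy can leave a severely hypocellular marrow, which is unevaluable in AML (10.6.8), or delay count recovery and cost a full CR. Leukemia that grew between an old marrow and Day 1 can be read as progression in ALL (10.7.5) and end treatment. The formula in step 4 leaves these effects out.
- **That remission is read from the marrow alone.** Blood, extramedullary sites and counts also enter.
- **That AML partial response is affected.** Section 10.6.5 excludes it from the response calculation.

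The maintenance route is also less clear than the table suggests. Section 3.3.2.3 excludes patients currently receiving other anti-cancer agents, with exceptions only for steroids and hydroxyurea, while 3.2.5.1(a) requires no wait after maintenance. The two passages need to be reconciled. Neither bars maintenance given after the marrow and ended before enrollment.

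Finally, a single r for such different treatments is crude. A patient with at least 5% blasts while on maintenance has disease despite it, so the assumed r may be too high there.

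**Conclusion.** The gap is real and follows from the text. The disease-defining marrow may precede effective therapy, and no response or evaluability rule allows for that, so a remission wholly or partly due to the therapy can enter the aim 1.3.3 rate. The frequency is unknown. The net direction is probably upward, because the permitted drugs are anti-leukemic, but it is not certain.

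The windows in step 2 need no assumption beyond a Day -28 marrow. The rates in steps 4 and 5 illustrate what the gap could do and are not estimates. The primary Cohort A response rate does not depend on any of this. It is a reporting weakness in an exploratory aim, worth correcting because the correction is cheap.

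**What to change.** Add to Section 9, for aim 1.3.3:

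- Report the overall CR/CRi rate among all evaluable Cohort C patients.
- Report it separately for patients with and without systemic anti-leukemia therapy between the qualifying marrow and Day 1, each group with its own numerator and denominator. If numbers are very small, give a patient listing showing the marrow date, the therapy and its last date, and the response.
- Rest any statement about larotrectinib-induced remission on the unexposed group.
- Do not recode exposed remissions as failures, for the reason in step 6.

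Exposure can be derived by comparing the last systemic dose date with the marrow date. Section 3.2 already requires the data behind eligibility to be in the record. No patient is dropped, no procedure is added and no treatment rule changes.

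The cost is smaller subgroups and a less precise, perhaps less favourable, attributable rate. The groups are not randomized, so the unexposed rate describes those patients only. Changing the marrow timing is not a substitute. With accrual complete it would have no effect. It could also require a second marrow, because steroids and hydroxyurea may continue after enrollment until 24 hours before the first dose.

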3.2.3 Disease Status

- i. Solid Tumors (Cohorts A & B): Patients must have measurable disease (see Section [10.3.1](#) for definition). Patients must have disease that cannot be completely resected without a predicted functional, neurologic, or significant cosmetic deficit in the opinion of the investigator.
- ii. Leukemia (Cohort C): Patients must have $\geq 5\%$ blasts in the bone marrow. Extramedullary disease is permitted.

3.2.4 Performance Level

Patients must have a Lansky or Karnofsky performance status score of ≥ 50 , corresponding to ECOG categories 0, 1 or 2. Use Karnofsky for patients > 16 years of age and Lansky for patients ≤ 16 years of age. **NOTE:** Neurologic deficits in patients with CNS tumors must have been stable for at least 7 days prior to study enrollment. Patients who are unable to walk because of paralysis, but who are up in a wheelchair, will be considered ambulatory for the purpose of assessing the performance score.
(See [Appendix IX](#))

3.2.5 Prior Therapy

- Cohorts A & B: No prior anti-cancer therapy, including radiotherapy, other than surgical resection is permitted.
 - Patients who experience recurrence after surgery alone and no other anti-cancer therapy will be eligible.
 - If not eligible due to prior anticancer therapy, patients may be eligible for the larotrectinib arm of Pediatric MATCH (APEC1621A) or treatment with commercial larotrectinib off study.
- Cohort C: The following apply to patients with relapsed/refractory leukemia:
 - 3.2.5.1 Patients with relapsed leukemia (Cohort C) must have fully recovered from the acute toxic effects of all prior anti-cancer therapy and must meet the following minimum duration from prior anti-cancer directed therapy prior to enrollment. If after the required timeframe, the numerical eligibility criteria are met, e.g. blood count criteria, the patient is considered to have recovered adequately.
 - a. Cytotoxic chemotherapy or other anti-cancer agents known to be myelosuppressive. See DVL homepage for the Myelosuppressive, Non-Myelosuppressive, and Antibody Anti-Cancer Agents table (<https://cogmembers.org/Site/Disc/DevTherapeutics/Default.aspx>). For agents not listed, the duration of this interval must be discussed with the study chair and the study-assigned Research Coordinator prior to enrollment.
 - A waiting period prior to enrollment is not required for patients receiving standard cytotoxic maintenance chemotherapy (i.e., corticosteroid, vincristine, 6MP, and/or methotrexate).
 - A waiting period is not required for patients receiving a single dose of intrathecal methotrexate, hydrocortisone, and/or cytarabine within 7 days prior to enrollment
 - ≥ 14 days must have elapsed after the completion of other cytotoxic therapy, with the exception of hydroxyurea, for patients not receiving standard maintenance therapy. Additionally, patients must have fully recovered from all acute toxic effects of prior therapy.

Note: Cytoreduction with hydroxyurea must be discontinued ≥ 24 hours prior to the start of protocol therapy.

- b. Anti-cancer agents not known to be myelosuppressive (e.g., not associated with reduced platelet or ANC counts): ≥ 7 days after the last dose of agent. See DVL homepage for the Myelosuppressive, Non-Myelosuppressive, and Antibody Anti-Cancer Agents table (<https://cogmembers.org/Site/Disc/DevTherapeutics/Default.aspx>). For agents not listed, the duration of this interval must be discussed with the study chair and the study-assigned Research Coordinator

prior to enrollment.

- c. Anti-cancer agents that are antibodies: ≥ 21 days must have elapsed from infusion of last dose of antibody, and toxicity related to prior antibody therapy must be recovered to Grade ≤ 1 . There is an exception for blinatumomab infusions, for which patients must have been off for at least 3 days and all drug related toxicity must have resolved to Grade 2 or lower as outlined in the inclusion/exclusion criteria. See DVL Homepage for the Myelosuppressive, Non-Myelosuppressive, and Antibody Anti-Cancer Agents table (<https://cogmembers.org/Site/Disc/DevTherapeutics/Default.aspx>).
- d. Corticosteroids: See Section 3.3.2.1. If used to modify immune adverse events related to prior therapy, ≥ 14 days must have elapsed since last dose of corticosteroid. A waiting period prior to enrollment is not required for patients receiving corticosteroid for leukemia therapy/cytoreduction.
- e. Hematopoietic growth factors: ≥ 14 days after the last dose of a long-acting growth factor (e.g. pegfilgrastim) or 7 days for short-acting growth factor. For agents that have known adverse events occurring beyond 7 days after administration, this period must be extended beyond the time during which adverse events are known to occur. The duration of this interval must be discussed with the study chair and the study-assigned Research Coordinator.
- f. Interleukins, Interferons and Cytokines (other than Hematopoietic Growth Factors): ≥ 21 days after the completion of interleukins, interferon or cytokines (other than Hematopoietic Growth Factors)
- g. Stem cell Infusions (with or without TBI):
 - Allogeneic (non-autologous) bone marrow or stem cell transplant, or any stem cell infusion including DLI or boost infusion: ≥ 84 days after infusion and no evidence of GVHD.
 - Autologous stem cell infusion including boost infusion: ≥ 42 days.
- h. Cellular Therapy: ≥ 42 days after the completion of any type of cellular therapy (e.g., modified T cells, NK cells, dendritic cells, etc.)
- i. XRT/External Beam Irradiation including Protons: ≥ 14 days after local XRT; ≥ 150 days after TBI, craniospinal XRT or if radiation to $\geq 50\%$ of the pelvis; ≥ 42 days if other substantial BM radiation.
- j. Radiopharmaceutical therapy (e.g., radiolabeled antibody): ≥ 42 days after systemically administered radiopharmaceutical therapy.
- k. Patients must not have received prior exposure to TRK inhibitors (including larotrectinib, LOXO-195, entrectinib, lorlatinib, crizotinib,

or lestaurtinib).

